7.3.4. Suspected Unexpected Serious Adverse Reaction (SUSAR)

All SUSARs will be reported by the Sponsor or delegate to the relevant Competent Authority (CA) (EudraVigilance database) and to the Ethics Committee and other parties as applicable. For fatal and life-threatening SUSARs, this will be done no later than seven calendar days after the Sponsor or delegate is first aware of the reaction. Any additional relevant information will be reported within eight calendar days of the initial report. All other SUSARs will be reported within 15 calendar days.

This study is an investigator initiated non-commercial study where the PI lacks the ability to report directly into the European database of side effects (EudraVigilance) and we therefore ask CA for help. SUSAR is reported via CIOMS-form.

7.3.5. Annual Safety Report

A safety report will be completed by the Sponsor once a year and sent to the relevant CA and the EC. The document will define the time period reported and summarize all occurred serious events (SAEs and SUSARs). The safety report should also always include a summary assessment of the safety of subjects that are still included in the trial and whether the benefit-risk assessment changed since the study was approved.

8. STATISTICS

8.1. Sample size calculation

The sample size calculation is made for the primary objective described in section “2 Study Objectives and Endpoints”.

- We assume these selected older individuals will have an average of two courses of antibiotics for suspected UTI every six months (4).
- We assume a 25% reduction of antibiotic prescriptions during the first six-month period after introduction of methenamine hippurate. Hence the intervention group would have an average of 1.5 while the control group is assumed to remain around 2.0. We assume the standard deviation in each group to be 1.5. This will result in an effect size of 0.33 (small effect). We decided a smaller effect size would not be worth looking for.
- We assume the level of significance being 0.05, the power to be 0.80 and that a two tailed test is explored.
- We use Student's t-test as the statistical analysis but also calculate for Mann-Whitneys test (to be used if the outcome variable is not normally distributed). The planned statistical method to be used will be multivariate linear regression. Student's t-test and Mann-Whitneys test are used as surrogate methods to estimate sample size.

Under the assumptions given above an effective sample size of 286 patients (143+143) is required if t-test can be used. However, if Mann-Whitney's test is required we need 298 (149+149) patients. To achieve an effective sample size of at least 298 after considering a 25% loss to follow-up we aim to include at least 397 patients. We will aim to include 400 patients.

8.2. Statistical analysis

It is the intention to adjust all analysis for the following confounding variables obtained at visit 1

- patient's age
- urine acidity (pH)
- number of antibiotic courses for UTIs in the 12 months preceding inclusion in the study
- presence of urease/stone-producing bacteria in urine culture day 1 such as proteus, some klebsiella species, Morganella morganii, Corynebacterium urealyticum and providencia

- use of local oestrogen
- patient has diabetes mellitus
- obesity defines as BMI ≥ 30
- presence of known mild abnormality of the urogenital tract
- if the patient is sexually active.
- If the patient previously have experienced urinary tract stone

Phylogenetic subtype of pure cultures of E.coli in the urine culture at inclusion will be analysed in a separate analysis if the number of cultures available for typing are not too small.

The statistical calculation relates to the study objectives described in section “2 Study Objectives and Endpoints”:

- 1 Standard linear regression will be used where number of UTI antibiotic treatments will be the dependent variable. Group allocation together with the confounding variables above will be independent variables. The dependent variable will be transformed using a rank transformation in case it is not normally distributed. A p-value will be delivered but no useful effect size if a rank transformation is used.
- 2a Will be analysed using the same statistical approach as objective 1 above.
- 2b Will be analysed using the same statistical approach as objective 1 above. Number of UTIs will be the dependent variable.
- 2c The outcome variable is measured at first day of a UTI using a six grade ordinal scale. The median value from all UTIs will be used if the patient has more than one episode of UTI. The dependent variable will be transformed using a rank transformation. It will be analysed using linear regression using the same covariates as when analysing objective 1. This will deliver a p-value but no useful effect size.
- 2d Will be analysed using the same statistical approach as objective 1 above. Number of days with symptoms will be the dependent variable.
- 2e Will be analysed using the same statistical approach as objective 1 above. Number of severe events such as pyelonephritis or hospital admission will be the dependent variable.
- 2f Phylogenetic subtype of pure cultures of E.coli in the inclusion urine culture at inclusion will be analysed in a separate statistical analysis if the number of cultures available for typing are at least 60 patients. All statistical above will be redone adding phylotype as an extra independent variable. Purely descriptive statistics will be presented in case the number is below 60.

Intention to treat analysis and missing data

The primary statistical analysis is intention to treat. Patients leaving the study completing only a part of the first six months will contribute with data up until they leave the study. Their data will be recalculated as if they had participated all six months. Patients leaving during the second six months period will also contribute with data as above. Patients leaving the study before the second six-month period commence will have their value for this period set to be the median value for both groups.

Complete case analysis

A complete case analysis will also be made where only patients having a complete data set will be included.

Per protocol analysis

A per protocol analysis will not be made.

9. DATA MANAGEMENT

9.1. Recording of data

The investigator will ensure that all data collected in the study are recorded in a timely manner according to any instructions provided. An electronic Case Report Form (eCRF) will be used for data collection. The investigator will ensure that the data are recorded and that any corrections in the CRF as specified in the study protocol and in accordance with the instructions provided. The investigator ensures the accuracy, completeness and timeliness of the data recorded.

Research Online (RO) is an electronic data capture (EDC) system that will be used for data collection. Web-based case report forms (eCRF) are implemented into the system to facilitate the study specific data collection. These forms can easily be accessed by all standard web browsers. The baseline CRF at inclusion, telephone follow-up in case of acute UTI episode(s), telephone contact by end of treatment, telephone contact by end of study and SAE Forms will be entered onto this system. Some sites may choose to first register data in a paper version of the CRF that will later be entered into the eCRF by the coordinating centre. The investigator will sign the completed CRF. A copy of a completed paper CRF will be archived at the study site. The original paper CRF will be archived at the coordinating centre in each country.

Multiple validation and range checks will be programmed in the eCRF to assure complete and high-quality data. Data that does not comply with these rules or ranges will generate a query that must be resolved immediately or at a later stage. Electronic workflows will employ multiple skip and jump rules to ensure that only information that is applicable to the patient will appear. After the data of the last subject is entered, the clean file will be produced and thereafter the database will be closed and data made available for further analysis and publication purposes.

RO meets all requirements according to GCP standards for electronic data entry with respect to safeguarding data integrity and data security regulations. Users will have role-based access to the system by logging in using their personal username and password. The system will log all data entry steps with timestamps and user information. The role-based access to the system will avoid unauthorised data access and prevents users from performing actions that they do not have authorisation for.

Project management of the study is facilitated by the integrated real live study progress reports. RO data traffic over the Internet is encrypted using secured data communication protocols. Dedicated databases and web servers are hosted in a secure data centre, the database (PostgreSQL) is backed up on a daily basis.

Participants will be identified by a unique trial specific number and/or code in any database. The name and any other identifying detail will not be included in any trial data electronic file, only within a separate password protected administration database.

9.1.1. Source data

The investigator must maintain source documents for each subject in the study. A source data verification log will be included in the Investigator Study File (ISF). The investigator must ensure that all source documents are accessible for monitoring.

Source documents are original documents, data, and records from which participants' CRF data are obtained. These include, but are not limited to, general practice and hospital medical records. CRF entries will be considered source data if the CRF is the site of the original recording (e.g. there is no other written or electronic record of data). In this study the CRF will be used as the source document for the documentation of inclusion and exclusion criteria, and baseline assessment information (visit 1), which will include, but not be limited to, comorbidities (see point 3.4. study assessment visit 1) and severity of UTI-symptoms.

All documents will be stored safely in confidential conditions. On all study-specific documents, other than the signed consent and contact details form, the participant will be referred to by the study participant ID, not by name. Requested reports from medical records and laboratory results will be entered into CRF.

9.2. Data storage and management

All data should be recorded, handled and stored in a way that allows its accurate reporting, interpretation and verification. All source data including informed consent, a copy of the completed CRF, original protocol with amendments and the final report will be stored at the coordinating centres for a minimum period of fifteen years after termination of the trial, in accordance with country specific regulation/law.

Staff designated by the Sponsor will review the data entered into the CRFs by investigational staff for completeness and accuracy and instruct the site personnel to make any required corrections or additions. Queries are issued electronically. Designated investigator site staff is required to respond to the query and confirm or correct the data.

At the conclusion of the study, the occurrence of any protocol deviations will be determined. After these actions have been completed and the database has been declared to be complete and accurate, it will be locked and available for data analysis.

Direct access will be granted to authorised representatives from the Sponsor, host institution and the regulatory authorities to permit trial-related monitoring, audits and inspections.

10. QUALITY CONTROL AND QUALITY ASSURANCE

10.1. Monitoring

A study monitor will be appointed by the sponsor. The monitor will be appropriately trained and informed about the nature of the study, subject written information, GCP and applicable regulatory requirements. The monitor's qualifications will be documented. Monitor [name] will

monitor the study in all 4 countries, and separate agreements between monitor and PI in each country will be made.

The quality control of this study will have a risk-based approach. The monitor will have regular contacts with the clinic to verify informed consents of participating subjects, to confirm that facilities remain acceptable, that the investigational team is adhering to the protocol, that data are being accurately recorded in the CRFs, to verify inclusion/exclusion criteria, study main endpoints, check SAE reporting and that therapy accountability is being carried out. The investigator should ensure that all persons assisting with the trial are adequately informed and trained about the protocol, the investigational product(s) and their trial related duties and functions. The monitor will check that training has been performed and that this is documented. The monitor will also ensure source data verification (comparison of the data in the CRF with the medical records and other source data). The monitor must have direct access to source data. The extent of monitoring will be defined in a monitoring plan.

10.2. Audits and inspections

Authorized representatives of the sponsor, a Competent Authority or an Ethics Committee may perform audits or inspection at the centre, including source data verification. The investigator must ensure that all source documents are accessible for auditing and inspection. The purpose of an audit or inspection is to systematically and independently examine all study-related activities and documents, to determine whether these activities were conducted, and data were recorded, analysed and accurately reported according to the protocol, Good Clinical Practice (GCP) and any applicable regulatory requirements.

10.3. Data safety monitoring committee

A data safety monitoring committee will be established and will consist of 3 external researchers with experience from clinical trials on UTI infections in primary care. They will meet every 6 months during the trial to ensure data safety. For premature termination of the study, see 4.2.2.

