- able and willing to comply with all trial requirements
- able and willing to give informed consent

Exclusion criteria:

- the patient has taken methenamine hippurate within the last 12 months
- the patient is allergic to methenamine hippurate
- the patient is having current antibiotic prophylaxis for UTI
- the patient has a urinary catheter (chronic indwelling catheters as well as intermittent urinary catheterisation)
- the patient has known severe chronic renal failure or estimated creatinine glomerular filtration rate ≤ 30 ml/min (known = registered in GP clinical records)
- the patient has a known condition or treatment associated with significant impaired immunity (e.g. long-term oral steroids, chemotherapy, or immune disorder) (known = registered in GP clinical records)
- the patient has a known severe hepatic impairment (known = registered in GP clinical records)
- the patient is suffering from severe dehydration
- the patient has gout
- the patient has a need for long term use of antacids such as magnesium hydroxide, magnesium carbonate, aluminium hydroxide
- the patient has a life expectancy estimated by a clinician to be less than six months
- the patient has been involved in, including completion of, follow-up procedures, in another clinical trial of an investigational medicinal product in the last 90 days
- the patient suffers from incontinence too severe to be able to provide a voided urine specimen
- the patient is participating in ImpresU Work Package 2
- the patient is suffering from significant known abnormal renal tract anatomy/physiology (i.e. single kidney, persistent urinary tract stone disease, severe vesicoureteral reflux) or neuropathic bladder disorders
- lactose intolerance.

Premature termination of the study

The difference between groups in SAEs deemed to be linked to possible treatment with methenamine hippurate will be continuously monitored without breaking the code. The study will be terminated in case there are significantly more SAEs within one of the groups during the trial.

Investigational product, dosage and administration: Methenamine hippurate 1 gram or placebo per os morning and evening day 1-180.

[figure not shown]
Primary outcome variables and examinations: Number of UTI courses during day 2-180

Study period: 1 November 2019 to 31 December 2022.

SIGNATURE PAGE

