4.4.2. Premature termination of the study

The difference between groups in SAEs deemed to be linked to methenamine hippurate will be continuously monitored (appendix 5). The study will be terminated if there is a significant difference between the two trial arms regarding SAE, SAR and SUSAR probably or definitely related to the trial medication or UTI. This will be done by comparing the two groups without breaking the code. The code will be broken if the difference between groups in these adverse effects are statistically significant ($p<0.05$). The study will be prematurely terminated if the statistical difference is to the disadvantage of active IMP. SAE, SAR and SUSAR possibly related to the trial medication or UTI will be registered but not used for decision making for eventual premature termination of the study. The investigator will promptly inform the participants, the Ethics Committee (EC) and other relevant regulatory authorities according to national regulations providing a detailed written explanation.

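### The external safety committee has no stated remit, and the only written group-level stopping trigger is p<0.05 on an unnamed test, which is insensitive to rare drug-related serious events

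*Protocol*

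**What the plan says.** Protocol 10.3 establishes a committee of three external researchers. On their work it says: "They will meet every 6 months during the trial to ensure data safety. For premature termination of the study, see 4.2.2". It does not state what they look at, whether data come by group, what they may recommend, or to whom.

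Section 4.2 is the list of exclusion criteria and has no subsections. The rule stands under "4.4.2. Premature termination of the study", which makes no mention of the committee. It has these parts:

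- The groups are compared on an ongoing basis; the Synopsis says this "will be continuously monitored without breaking the code".
- The comparison is made "regarding SAE, SAR and SUSAR probably or definitely related to the trial medication or UTI".
- The code is broken when the difference reaches p<0.05. Then: "The study will be prematurely terminated if the statistical difference is to the disadvantage of active IMP".
- Lower-graded events are set aside: "SAE, SAR and SUSAR possibly related to the trial medication or UTI will be registered but not used for decision making".

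Neither the test nor its sidedness is given there, and the SAP's statistics section does not cover this comparison. The Synopsis words the rule differently: termination follows significantly more SAEs in either group, with no condition on direction.

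**The concern.** A significance test is a poor sole trigger for events that placebo can hardly cause. Section 1.3 rates the risk as very small, and 7.3.3 expects no previously unknown serious event. A few SAEs judged probably or definitely due to the drug would contradict that premise in women aged 70 or over taking a preventive treatment. Non-serious events are not recorded (6.3), so SAEs carry most of the safety information.

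The protocol already has an independent body that could weigh such events, but the text gives it no part in the decision. The text also names nobody to run the between-group comparison.

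**Working it through.** **The plan's own figure.** There is none to reproduce. The only number attached to the rule is the 0.05 threshold.

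**Inputs**

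- 200 women per arm at full enrolment (Protocol 5.1: 200 sets of boxes of each kind).
- Threshold 0.05 (4.4.2).
- Assumed, because the documents give neither: the test, and a true risk on active of 1%, 2% or 3% for SAEs probably or definitely due to the drug (2, 4 or 6 expected among 200), with none on placebo.

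**Step 1: which splits reach p<0.05?** For a split of a to 0 with 200 per arm:

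- Fisher, two-sided: p = 2 × C(200,a) / C(400,a). The one-sided value is half of this.
- Pearson without continuity correction: X² = 400a / (400 − a), compared with 3.841. For a = 3, 1200/397 = 3.02; for a = 4, 1600/396 = 4.04; for a = 5, 2000/395 = 5.06.

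| Split (active–placebo) | Fisher two-sided | Fisher one-sided | Pearson uncorrected |
|---|---|---|---|
| 3–0 | 0.248 | 0.124 | 0.082 |
| 4–0 | 0.123 | 0.062 | 0.044 |
| 5–0 | 0.061 | 0.030 | 0.024 |
| 6–0 | 0.030 | 0.015 | 0.014 |
| 7–1 | 0.068 | 0.034 | 0.032 |
| 8–1 | 0.037 | 0.018 | 0.018 |

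Other tests also divide at 5–0. The exact binomial (0.0625), Yates-corrected chi-square (0.072) and Barnard (0.080) do not trigger. Boschloo (0.039) and the likelihood-ratio test (0.008) do, and the likelihood-ratio test would fire even at 3–0 (0.041).

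The result hardly depends on when the look is taken. With 50 to 200 women per arm, 5–0 gives 0.056 to 0.061 by two-sided Fisher and 0.022 to 0.024 by Pearson.

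**Step 2: chance that the rule fires by full enrolment.** With no placebo events, the count on active can only rise. Across those arm sizes the rule therefore fires once the count reaches the threshold a*, however often one looks. The chance is P(X ≥ a*) with X ~ Binomial(200, π).

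Example at π = 2%: the probabilities of 0 to 5 events are 0.0176, 0.0718, 0.1458, 0.1963, 0.1973 and 0.1579.

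- P(X ≥ 6) = 1 − 0.7867 = 0.213.
- P(X ≥ 4) = 1 − 0.4315 = 0.569.

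| Test (threshold) | π = 1% | π = 2% | π = 3% |
|---|---|---|---|
| Fisher two-sided (6–0) | 1.6% | 21% | 56% |
| Fisher one-sided (5–0) | 5% | 37% | 72% |
| Pearson uncorrected (4–0) | 14% | 57% | 85% |

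**Step 3: limits of the model.** The written rule also counts UTI-related SAEs, which can occur in both arms; step 2 leaves them out. Step 1 shows what one placebo event does under two-sided Fisher: the split needed goes from 6–0 to 8–1.

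**The case against.** **The test is not named.** A reader might infer that five drug-related serious events on active against none on placebo would set nothing in motion. The documents do not support that. With a one-sided Fisher or uncorrected Pearson test, 5–0 breaks the code and stops the trial. What stands is that the same data stop or do not stop the trial according to an unstated choice, and that with either Fisher or Pearson a 3–0 split does not trigger.

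**Other safeguards exist.** A reader might also infer that nobody can act before significance. That too goes beyond the text:

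- A woman with an SAE possibly due to the drug is withdrawn (4.4.1).
- An individual code can be broken for medical or safety reasons (5.2, 5.3).
- The investigator may remove a participant from treatment on clinical judgement (7.3.1).
- SUSARs go to the authority and the ethics committee within 7 or 15 days (7.3.4).
- The annual report reassesses benefit and risk (7.3.5).
- Changes that remove an immediate hazard need no prior approval (section 12).

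These work case by case or come from the sponsor. None is an independent by-group review with a stated power to recommend stopping.

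**Sufficient or necessary?** Section 4.4.2 says the study stops if the difference is significant; it does not say that this is the only possible ground. That is fair. But no other group-level ground is written, and possibly related events are expressly kept out of the decision.

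**False alarms.** Unadjusted repeated testing pulls the other way. Assuming six equally spaced two-sided looks and a normal approximation, the chance of at least one false signal is about 16%. This is a separate weakness, and it too argues for using p<0.05 as a prompt rather than an automatic rule.

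**Unseen material.** Section 4.4.2 cites the safety reporting flow-chart in appendix 5, which was not available. It may name an owner for the comparison. A committee charter may exist, but the documents mention none.

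**Conclusion.** The point holds for group-level review and trial termination. The wrong section number alone would be clerical. The substance is that the independent committee has no stated remit or link to the stopping rule, while that rule rests on an unspecified significance test and excludes possibly related events.

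Under the assumptions in the working, a true drug-related SAE risk of 1% would trigger the rule with probability 1.6% to 14% between two-sided Fisher and uncorrected Pearson; at 2% the range is 21% to 57%, and at 3% it is 56% to 85%. A more liberal test would give higher figures. These figures rest on 200 women per arm, no qualifying placebo events, and no UTI-related events in the count. They illustrate how insensitive the trigger is and are not forecasts for this trial.

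**What to change.** 1. In 10.3, change the reference to 4.4.2.
2. In 10.3 and 4.4.2, state that the committee receives a listing of all reported SAEs by masked group, including those graded possibly related, at each six-monthly meeting and after any SAE judged related to the trial medication.
3. State that the committee may request unmasking and recommends continuing or stopping on its own judgement. Name the test and its sidedness, and make p<0.05 a prompt for review and not a precondition.
4. State that the trial team and the country PIs who judge relatedness (7.3.3) do not see the by-group listing. Section 5.2 already conceals allocation, but it does not say who may see a tally by masked group.

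While editing, reconcile two related passages: the Synopsis and 4.4.2 differ on direction, and 7.2.1 has no probable or definite grade although 4.4.2 relies on both.

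Cost: wording in two sections and a short listing twice a year. The committee exists, and 4.4.2 already requires the by-group comparison. The downside is a less mechanical rule, with a small chance of a recommendation based on few events. If follow-up is already complete, the study report should instead say what the committee saw, who made the comparison and with which test.
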